1.4 Description of the Products Under Study

1.4.1. Prevena™ Customizable™ Dressing Kit

Prevena™ Customizable™ Dressing or Prevena Plus™ Customizable™ Dressing kits will be provided by KCI as the study product to be tested in this study and will be labeled as

“Investigational Use Only” per FDA requirements. Instructions for use will be provided to each site.

[figure not shown]
The contents of the kit are listed below (shown in Figure 1):

- Prevena™ Customizable™ Dressing or Prevena Plus™ Customizable™ Dressing sealing strips
- drape
- ruler
- indicator or SensaT.R.A.C.™ pad with tubing
- tubing connector for V.A.C. units (if needed)

Figure 1. Prevena™ Customizable™ Dressing Kit Contents

Prevena Plus™ Customizable™ Dressing Kit

Prevena™ Customizable™ Dressing Kit

1.4.3 Prevena™ Customizable™ Dressing Description

The Prevena™ Customizable™ Dressing is a unique design that gives the clinician the freedom to alter the dressing to cover closed surgical incisions of different sizes and shapes (Figure 2). It is a predicate to and substantially equivalent to the Prevena™ Peel and Place dressing, which should not be altered to fit a closed incision.

The Prevena™ Customizable™ Dressing or Prevena Plus™ Customizable™ Dressing, in conjunction with NPWT, is intended to manage the environment of closed surgical incisions which continue to drain following sutured or stapled closure. The dressing provides a seal

around the incision site, maintains a closed environment, and removes exudate via the application of NPWT.

Figure 2. Prevena™ Customizable™ Dressing or Prevena Plus™ Customizable™ Dressing

While the Prevena™ Customizable™ Dressing was primarily developed for use with the Prevena™ unit and Prevena Plus™ Customizable™ Dressing was primarily developed for use with the Prevena Plus™ unit as the NPWT delivery method, the dressings have been designed to be compatible with V.A.C. Therapy Units as well. The Prevena™ Customizable™ Dressing or the Prevena Plus™ Customizable™ Dressing may be connected to the NPWT device of choice. The NPWT device creates a negative pressure vacuum of 125 mmHg relative to the closed surgical incision and causes exudate to be pumped into a collection canister attached to the NPWT device. The Prevena™ Customizable™ Dressing is constructed of three layers, as described in Table 1.

Table 1. Prevena™ Customizable™ Dressing Description

Layer/Material	Function
Skin Interface layer (Subject skin contacting)	
• Wicking Interface Fabric (polyurethane-coated polyester fabric with 0.019% silver)	Placed directly over the incision. Wicks fluid away from the skin/tissue; contains silver ions to reduce potential for contamination of the fabric with microbes.
• Polyurethane film with acrylic adhesive	Secures dressing to application site on Subject
Hydrocolloid Ring (Subject skin contacting)	
• Hydrophilic polymer ring attached to the outside edge of the foam bolster	Assists with dressing application and helps reduce dressing leaks
Foam Bolster (Subject skin non-contacting)	

• Polyurethane foam with pigment violet 23	Manifolds negative pressure to the surgical incision area through the underlying interface fabric
• Polyurethane film shell	Maintains the negative pressure environment in conjunction with the therapy unit
Pressure Pad with Sterile Tubing (Subject skin non-contacting)	
• Polyurethane film with acrylic adhesive	Connects dressing to the therapy unit, transfers negative pressure and removes exudate
• DEHP-free PVC, medical grade	

1.4.4 ActiV.A.C. Therapy System Description

The ActiV.A.C.® Therapy System is an electric and battery powered device that delivers continuous or intermittent negative pressure to a wound in the selectable range of 25mmHg to 200mmHg. A 300 mL canister is attached to the device to collect wound fluid.

The ActiV.A.C.® Therapy System is intended to create an environment that promotes wound healing by secondary or delayed primary intention. The application of NPWT prepares the wound bed for closure, reduces edema, promotes granulation tissue formation and perfusion, and removes exudate and infectious material. It is designed to be used in conjunction with all KCI dressing products including the Prevena™ Customizable™ Dressing or the Prevena Plus™ Customizable™ Dressing.

The ActiV.A.C. Therapy System will be the NPWT delivery method for this study. The device will be attached to the Prevena™ Customizable™ Dressing or the Prevena Plus™ Customizable™ Dressing immediately after the dressing is applied to the Subject's closed incision, and programmed to deliver continuous 125 mm/Hg negative pressure for the duration of study treatment.

Figure 3. ActiV.A.C. .® Therapy Unit

1.5 Regulatory Status of the Study Product

The Prevena™ Customizable™ Dressing provides a new dressing configuration that has been designed to allow the clinician to cut the dressing to fit the incision size and geometry. The Prevena™ Customizable™ Dressing and the Prevena Plus™ Customizable™ Dressing have received 510(k) clearance by the Food and Drug Administration (FDA) and are substantially equivalent.

The Prevena™ Customizable™ Dressing or the Prevena Plus™ Customizable™ Dressing Kit is intended to manage the environment of surgical incisions that continue to drain following sutured or stapled closure by maintaining a closed environment and removing exudate via the application of NPWT. The dressing should be applied to the closed incision immediately after surgery, connected to NPWT, and then remain in place for a minimum of 2 days up to a maximum of 7 days.

1.6 Performance Data of the Study Product

Performance testing demonstrates that NPWT is distributed throughout the Prevena™ Customizable™ Dressing when applied to its maximum length. In bench testing, pressure measurements were taken across the entire length of the dressing under wet and dry simulated wound conditions, meeting performance criteria.

Additionally, performance testing established that the Prevena™ Customizable™ Dressing is compatible with marketed V.A.C. Therapy units. When connected to an ActiV.A.C. Therapy Unit, negative pressure was distributed across the entire length of the dressing under wet and dry simulated wound conditions. Performance criteria were met successfully.

1.7 Clinical Data to Date

During the design phase of the Prevena™ Customizable™ Dressing, different dressing prototypes were tested in two healthy human clinical trials with the primary objective of evaluating leak rate of the dressings.

Results of the initial healthy human study exhibited relatively high leak rates of prototype dressings applied to the intact skin of Subjects, which were attributed to a manufacturing defect at the junction of the indication pad and tubing. The study also assessed possible skin reactions to dressing application with mild erythema reported as the most common skin reaction. When the dressing was cut and joined together, there were reports of occasional excoriation to the skin directly underneath the junction. Presumably, this was due to skin pinching between the two foam ends when NPWT was applied. To mitigate this issue, the use of sealing strips at foam ends or joins was proposed for a second healthy human study.

Leak rate and skin response data were collected as part of the second healthy human study, in which three different dressing application configurations were evaluated. All Subjects completed the study with no reports of severe or serious skin reactions; there was one report of skin hyperpigmentation. The addition of a hydrocolloid strip to the foam ends and joins was successful in mitigating the occurrence of skin excoriation. The three dressing configurations tested successfully passed the study's established leak rate parameters.

1.8 Rationale for Study Design and Risk/Benefits

The current literature does not have consistent definitions or measures of surgical site complications (SSC) for large incisions resulting from primary closure of an abdominal surgical procedure. Therefore, it is difficult to assess the true rate of these complications and the impact on health care resources.

Patients undergoing a functional panniculectomy procedure are left with a transverse surgical incision which spans from hip to hip, and depending on other procedures which may be performed at the same time, the patient may have a vertical incision in addition to the transverse incision, which overall looks like an inverted T (fleur-de-lis). Patients undergoing incisional hernia repair are left with a vertical incision which can span from the ribcage to the umbilicus.

These large incisions are not able to be covered by the Prevena™ Peel and Place dressing since the length is too short and the dressing cannot be altered. With Prevena™ Customizable™ Dressing or Prevena Plus™ Customizable™ Dressing, the extensive surgical incisions of abdominal surgery patients may now be covered and NPWT applied. The potential

clinical and economic benefits of prophylactic use of these dressings with NPWT for management of extensive abdominal surgical incisions have been explored, and clinical evidence to support its use in this patient population is warranted. Therefore, this study is proposed to evaluate and compare SSC incidence and collect safety data in Subjects receiving the Prevena™ Customizable™ Dressing or Prevena Plus™ Customizable™ Dressing versus a SOC surgical incision dressing to manage large closed surgical incisions resulting from abdominal surgery for incisional hernia repair and/or functional panniculectomy.

(Prevena™ Customizable™ Dressing or Prevena Plus™ Customizable™ Dressing will be referred to as “Customizable” from this point forward).

2 Study Objectives

The primary objective of the study is to compare surgical incision-related clinical outcomes in Subjects undergoing abdominal surgery for incisional hernia repair and/or functional panniculectomy when managed with Customizable as compared to SOC surgical incision dressing (dry sterile dressing/gauze, steri-strips).

Clinical outcomes of interest are dehiscence and surgical site infection (SSI) within 30 days post-surgical procedure. These short-term clinical outcomes are defined as the collective term SSC for the purposes of this study. SSC will be compared to a control group consisting of Subjects screened for the same inclusion and exclusion criteria but receiving SOC dressing. This study will also collect clinically relevant intervention (CRI) data.

2.1 Summary

The goal of this study is to evaluate the impact of Customizable in the management of extensive closed surgical incisions for Subjects undergoing abdominal surgery for incisional hernia repair and/or functional panniculectomy as compared to SOC dressing, and to significantly reduce the SSC rate experienced by Subjects receiving Customizable vs. SOC surgical incision dressing.

[figure not shown]
3 Study Design

This is a post-market, prospective, randomized controlled study to evaluate the safety and effectiveness of Customizable when used to manage extensive vertical, transverse, and fleur-de-lis surgical incisions resulting from the primary closure of incisional hernia repair and/or functional panniculectomy procedures. Study data will be analyzed for clinical outcomes through 30 days.

After approximately 60 Subjects have been enrolled and completed the study (ITT population); an interim data review will be performed to verify the study's sample size assumptions. If needed, the sample size may be increased to allow for enrollment of up to 500 Subjects (see Section 10.1, Sample Size Determination).

3.1 Design Summary

3.1.1 Study Design Schematic

3.1.2 Duration of Study Participation

Duration of Study participation per Subject is as follows:

- Screening: 45 days prior to and including Day 0 (day of surgery)

- Treatment Duration:
 - Customizable arm: 5 (+ 2) days
 - SOC arm: 2 (\pm 1) days
- Active Study Phase (after Randomization): Day 0 through 30 (\pm 4) days

The maximum participation duration per Subject is 80 days.

3.2 Primary Study Endpoint

Incidence of SSC with Customizable as compared to the control group receiving a SOC surgical incision dressing. For this study, a SSC is defined as one of the following:

- Dehiscence
- Surgical site infection (SSI)

3.3 Secondary Study Endpoint

3.3.1 Clinically Relevant Interventions

Incidence of clinically relevant interventions (CRI) of the surgical incision in Subjects managed with Customizable as compared to the control group managed with a SOC surgical incision dressing. For this study, clinically relevant interventions are defined as the following:

- Antimicrobial treatment of SSI
- Percutaneous and open drainage of the surgical incision (by surgeon)
- Debridement of the surgical incision
- Re-operation related to the surgical incision
- NPWT applied to the open surgical incision

3.4 Other Data Collected

Other data collected will include:

- Height, weight, BMI
- Panniculus weight, and grade using the following scale:

Grade 1	Panniculus barely covers the hairline of the mons pubis but not the genitalia .
Grade 2	Extends to cover the genitalia .

Grade 3	Extends to cover the upper thigh.
Grade 4	Extends to cover the mid thigh.
Grade 5	Extends to cover the knees or beyond.

Source: American Society of Plastic Surgeons [ASPS], 2007d

- Material used to reinforce hernia repair incision
- Incision type, location, and incision measurement in cm (measure vertical and transverse aspects of fleur-de-lis separately)
- SOC dressing materials
- Digital photographs of the closed surgical incision
- Customizable replacement (if required to maintain a seal)

3.5 Safety Endpoint(s)

All AEs will be tabulated and reported overall and by treatment arm.

3.6 Randomization Plan

This is a randomized controlled clinical trial. Randomization will occur intra-operatively after surgical incision closure and confirmation that all of the intra-operative inclusion criteria and none of the intra-operative exclusion criteria are met. Enrolled Subjects will be assigned to either Customizable or SOC surgical incision dressing in a 1:1 ratio stratified by incision type of either transverse/vertical or fleur-de-lis. Sealed randomization envelopes will be provided to the Investigator and will be used to obtain an intra-operative randomization assignment for each Subject. (Technical description of randomization is provided in Section 10.3). The assignment will be:

- Customizable arm; **or**
- SOC surgical incision dressing arm

4 Subject Selection

Subjects undergoing an abdominal surgery for incisional hernia repair and/or functional panniculectomy resulting in a vertical, transverse or fleur-de-lis incision, and who meet all inclusion and none of the exclusion criteria, will be enrolled in the study. No deviations or waivers of inclusion/exclusion criteria will be granted by KCI.

4.1 Inclusion Criteria

4.1.1 Pre-Operative Inclusion Criteria

The Subject:

1. Is an adult \geq 18 years old of either gender;
2. Is able to provide their own informed consent;
3. Will undergo:
 - a. A functional panniculectomy with a transverse or a fleur-de-lis incision;

– AND/OR –
 - b. An incisional hernia repair with a vertical incision at least 20 cm in length and at least 10 cm of undermining on each side of the incision;
4. Has a BMI \geq 30;
5. Has maintained a stable weight for at least 3 months as determined by the Investigator (applies to post weight loss patients only);
6. Is pre-operatively assessed to undergo a procedure with a CDC Wound Classification of:
 - a. Class I (Clean): An uninfected operative wound in which no inflammation is encountered and the respiratory, alimentary, genital or uninfected urinary tract is not entered;

– OR –
 - b. Class II (Clean Contaminated): An operative wound in which the respiratory, alimentary, genital or uninfected urinary tract are entered under controlled conditions and without unusual contamination;
7. Is willing and able to return for all scheduled study visits;
8. If a female of child-bearing potential, must test negative on a urine pregnancy test; and
9. If a female of child-bearing potential, must be willing to utilize an acceptable method of birth control (i.e. oral contraceptives, condom with spermicide, diaphragm with

spermicide, implants, IUD, injections, vaginal rings, hormonal skin patch) for the duration of the study

4.1.2 Intra-Operative Inclusion Criteria

Subjects must meet the following intra-operative inclusion criteria to be eligible for randomization.

The Subject:

1. Continues to meet all pre-operative inclusion criteria
2. Has undergone a Class I or II CDC Wound Classification procedure resulting in a closed surgical incision able to be covered completely by Customizable dressing

4.2 Exclusion Criteria

4.2.1 Pre-Operative Exclusion Criteria

The Subject:

1. Has a systemic bacterial or fungal infection at the time of surgery for incisional hernia repair and/or functional panniculectomy;
2. Has a remote-site skin infection at the time of surgery for incisional hernia repair or functional panniculectomy;
3. Is preoperatively assessed to undergo a procedure with a CDC Wound Classification of:
 - a. Class III (Contaminated): Open, fresh, accidental wounds, and/or major breaks in sterile technique or gross spillage from the gastrointestinal tract;
– OR –
 - b. Class IV (Dirty-Infected): Old traumatic wounds with retained devitalized tissue and those that involve existing clinical infection or perforated viscera;
4. Will have a transverse or fleur-de-lis incision that extends beyond the flank area and requires moving the Subject from the supine position during surgery;
5. Has a known allergy or hypersensitivity to silver, or drape materials that contain acrylic adhesives;
6. Has participated in a clinical study within the past 30 days; and

7. Who, in the investigator's opinion, would have any clinically significant condition that would impair the Subject's ability to comply with the study procedures

4.2.2 Intra-Operative Exclusion Criteria

Subjects who meet any of the following intra-operative exclusion criteria are considered screen failures and are not eligible for randomization.

The Subject:

1. Is found to meet any of the pre-operative exclusion criteria;
2. Is determined to have a CDC Wound Classification of:
 - a. Class III (Contaminated): Open, fresh, accidental wounds, and/or major breaks in sterile technique or gross spillage from the gastrointestinal tract;

– OR –
 - b. Class IV (Dirty-Infected): Old traumatic wounds with retained devitalized tissue and those that involve existing clinical infection or perforated viscera.

5 Study Procedures

5.1 Informed Consent

The Investigator will discuss the purpose of this study with potential Subjects. Each potential Subject will review the IRB-approved Informed Consent Form (ICF). The Subject and the Investigator (or designated medically licensed sub-investigator), must sign and date the ICF before the Subject can undergo any study-related procedures. The Subject's informed consent will be obtained under these conditions:

- Subjects must be made aware of the purpose of the study and the potential risks and benefits known or that can be reasonably predicted or expected;
- Subjects must be given the opportunity to ask the Investigator questions and must be provided time to consider participation in the study;
- ICFs will be written in a manner that is non-technical and understandable to the Subject;
- Subjects will not be led to believe that they are waiving their legal rights to release the Investigator, KCI, the Institution, or any of their agents from liability from negligence;

- Subjects will be asked to sign and date the ICF indicating their informed consent to be enrolled in the study;
- The Investigator's responsibilities during the ICF process include:
 - Screening out potential Subjects who may not be able or willing to comply with the clinical investigation protocol,
 - Ensuring that Subjects have signed and dated the ICF prior to undergoing any clinical investigation related procedures, and
 - Ensuring that each Subject receives a copy of their signed ICF.

5.2 Numbering of Study Subjects

After signing the ICF, the site will assign a unique, consecutive screening number to each Subject for screening log tracking purposes. At randomization, a Subject number will be assigned. The number will be a combination of the study site number (provided by KCI), followed by 1001 for transverse/vertical incisions and 2001 for fleur-de-lis incisions, and increasing sequentially in the stratum.

Once a Subject number is assigned, it is not to be re-assigned to another Subject. For example, if a Subject is randomized but does not receive study treatment and is withdrawn, limited Case Report Forms (CRFs) will be completed with the assigned Subject number, noting the reason(s) for withdrawal.

If a screened Subject does not meet the intra-operative inclusion criteria or meets any intra-operative exclusion criteria, the Subject will be considered a screen failure and the reason for the failure should be included in the screening log. If a Subject is rescreened, a new Screening number must be assigned.

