7.2.1 By Investigator

The Investigator may choose to discontinue the Subject from study with or without his/her consent for any of the following:

- AEs;
- Noncompliance; or
- Any reason that may, in the opinion of the Investigator, affect negatively the safety or well-being of the Subject.

If for any reason the Subject is withdrawn from the study, the Investigator will inform the Subject and KCI accordingly.

8 Risks Associated with Participation in the Study

Participation in this study presents low risks to Subjects. Risks associated with Customizable and the ActiV.A.C. Therapy Unit are generalized and are listed in Table 5 (Section 8.1).

8.1 Potential Risks Associated with Customizable and ActiV.A.C.

All risks known (based on prior relevant experience) or anticipated on reasonable grounds are listed. This table, and if needed this document, will be updated in the presence of new information of relevance to the safety of the Subject or the conduct of the study.

Table 5. Risks Associated with Customizable and ActiV.A.C.

Risks	Disorders/Conditions
Skin and Subcutaneous Tissue	
• Local cutaneous reaction (i.e. redness, rash, significant pruritis, urticaria)• Allergic reaction• Maceration• Minor soft tissue damage• Epidermal (skin) stripping• Minor bleeding• Pain• Contusion (bruising)
Other	
• Bleeding complications (associated with the surgical procedure, concomitant therapies and co-morbidities)• First degree burn (if device gets warm)• Exposure related infection• Localized infection• Physical discomfort• Minor desiccation (due to dressing leak)• Moderate soft tissue damage (i.e. due to trip hazard, tubing entanglement)• Deterioration of the wound (due to lack of visibility of incision site through dressing)

9 Safety and Adverse Events

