10.2 Subject Populations for Analysis

There are two principle analysis populations for this clinical study:

10.2.1 Full Analysis Set (FAS) Population – The FAS subject population will consist of all Subjects who i) met all of the pre-operative and intra-operative inclusion criteria and none of the pre-operative and intra-operative exclusion criteria, ii) have been randomized, and iii) received treatment with either Customizable or SOC dressing. Subjects without SSC will need to receive at least 5 days of Customizable or at least 1 day of SOC dressing to be included in this set and completed Visit 9/Day 30 (\pm 4 days). Subjects with SSC prior to Visit 9/ Day 30 (\pm 4 days) will be included in this set regardless of length of Customizable or SOC dressing treatment and treatment follow up. Subject data will be analyzed in the arm to which they were randomized and treated. The primary and secondary effectiveness analyses for this study will be based on the FAS population.

10.2.2 Safety Population (SP) / Intent-to-Treat (ITT) – The safety population / ITT will consist of all Subjects who are randomized and do not withdraw before the attempt to apply the assigned treatment with Customizable or SOC surgical incision dressing regardless of its duration. Subject data will be analyzed in the arm to which they were randomized. All safety results and supportive analyses for this study will be presented based on the safety population.

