10.3 Randomization

Subjects who meet all inclusion criteria and no exclusion criteria and who consent to participate in the study will be randomized in a 1:1 ratio to be treated with either Customizable or SOC surgical incision dressing. Due to the variances in complication rates between incision types, a stratified randomization will be used to ensure balance between the groups. The randomization will be stratified for each site and incision type of vertical/transverse and fleur-de-lis. Within each stratum, permuted blocks will be used to achieve equal numbers of Subjects assigned to Customizable or SOC surgical incision dressing. For each stratum, a randomization schedule will be generated to include Subject numbers and treatment assignments with the stratum of transverse/vertical incision starting with 1001 and the stratum of fleur-de-lis incision starting with 2001. Corresponding randomization envelopes will be prepared in sequential order by Subject number to provide randomization to each Investigator.

Randomization envelopes will be prepared corresponding to each row in the randomization schedule. Subject numbers will be printed and labeled clearly on the top of each envelope. Additionally, the envelopes will be color coded for incision type stratum, sealed, and organized by stratum and in ascending by Subject number

Once the Subject has been screened, deemed eligible, and provided informed consent, the next available sequentially numbered randomization envelope within the corresponding stratum according to incision type; a sealed Customizable box and ActiV.A.C. unit will be taken into the operating room with the Subject. Randomization will be conducted in the operating room after closure of the surgical incision and confirmation of intra-operative eligibility. The envelope will be opened prior to surgical incision dressing placement and the assigned treatment arm will be used. If Customizable is not selected, the sealed box and ActiV.A.C. unit will be returned to appropriate storage area.

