5.3 Analysis Populations

The following subject populations for this clinical study are:

Safety Population – The Safety population will consist of all subjects who are randomized and do not withdraw before the attempt to apply the assigned treatment with Customizable™ or SOC surgical incision dressing regardless of its duration. Subject data will be analyzed in the arm to which they were treated. All safety results for this study will be presented based on the safety population.

Intent-to-Treat (ITT) Population – The ITT population will consist of all subjects who are randomized and do not withdraw before the attempt to apply the assigned treatment with Customizable™ or SOC surgical incision dressing regardless of its duration. Subject data will be analyzed in the arm to which they were randomized. All supportive or exploratory analyses for this study will be presented based on the ITT population.

Full Analysis Population (FAS): The FAS subject population will consist of all subjects who i) met all of the pre-operative and intra-operative inclusion criteria and none of the pre-operative and intra-operative exclusion criteria, ii) have been randomized, and iii) received treatment with either Customizable™ or SOC dressing. Subjects without SSC will need to receive at least 5 days of Customizable™ or at least 1 day of SOC dressing to be included in this set and completed Day 30 (\pm 4 days). Subjects with SSC prior to Day 30 (\pm 4 days) will be included in this set regardless of length of Customizable™ or SOC dressing treatment and treatment follow up. Subject data will be analyzed in the arm to which they were randomized and treated. The primary and secondary effectiveness analyses for this study will be based on the FAS population.

Subjects having important disqualifying protocol deviations will be excluded from ITT and/or FAS based on the results from the protocol deviation review described in Section 5.4 of this document.

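### The population called ITT omits randomised subjects withdrawn before the dressing is attempted, when the arm is already known, so no effectiveness or safety population holds everyone randomised

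*Protocol*

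**What the plan says.** Protocol 10.2.2 uses one definition for the Safety and ITT populations: "all Subjects who are randomized and do not withdraw before the attempt to apply the assigned treatment". SAP 5.3 separates the two but gives both the same condition; for ITT it reads "The ITT population will consist of all subjects who are randomized and do not withdraw before the attempt to apply the assigned treatment". The FAS, which carries the primary analysis, requires among other things that the subject "received treatment with either Customizable or SOC dressing". The ITT analysis is the planned support for the FAS result (Protocol 10.5.1, SAP 7.1).

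Randomisation takes place in the operating room once the incision is closed and intra-operative eligibility is confirmed, and the envelope is opened before the dressing goes on (Protocol 3.6, 10.3). SAP 2 calls the trial open-label.

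Protocol 7.2 lets the investigator withdraw a subject at any time on safety, behavioural or administrative grounds. Protocol 7.2.1 adds: "The Investigator may choose to discontinue the Subject from study with or without his/her consent", for adverse events, noncompliance or anything judged to harm safety or well-being.

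For the subject in question, Protocol 5.2 states that "if a Subject is randomized but does not receive study treatment and is withdrawn, limited Case Report Forms (CRFs) will be completed", with the reason for withdrawal noted.

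**The concern.** An ITT analysis protects the comparison because nobody leaves it for a reason that could depend on the assigned arm. Here the definition allows exactly that. Eligibility is settled before the envelope is opened, so it should not be a reason to drop a subject between opening and dressing placement. In that interval the subject is still in the operating room, and the person in a position to end participation is the investigator, who has just learned the arm and will later assess SSC.

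If the decision depended on how difficult the incision looked for the assigned dressing, it would be related to prognosis. The FAS would lose the subject and so would the ITT analysis, so the supportive analysis could not reveal the problem. This differs from the separate questions of disqualifying protocol deviations and of dressings that end early, both of which arise after treatment starts or through another rule.

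**Working it through.** **1. Where a randomised, untreated subject is counted**

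| Place | Condition for entry | Withdrawn before the attempt? |
|---|---|---|
| FAS (Protocol 10.2.1, SAP 5.3) | Randomised, eligible, treatment received | Out |
| ITT (Protocol 10.2.2, SAP 5.3) | Randomised, not withdrawn before the attempt | Out |
| Safety (same sections) | As ITT | Out |
| Disposition table and CONSORT (SAP 6.1) | Randomised, by treatment group | In |

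Protocol 10.9 has no imputation algorithm and SAP 5.4.1 imputes only partial dates, so no later step brings the subject back into an endpoint analysis.

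**2. What is collected**

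Protocol 5.2 asks for limited CRFs without saying which. Protocol 7.2 asks for every effort to document outcome and for a final visit if applicable, and the early withdrawal visit (Protocol 6.10) includes SSC and CRI items as applicable. Neither commits to the Day 10, 14, 21 and 30 assessments.

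**3. The plan's own figure**

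Inputs from Protocol 10.1: 35% SOC, 8.75% Customizable, 44 per arm, two-sided Fisher's exact test at 0.05. Enumerating all binomial outcomes gives power of 80.7%, against the stated figure of about 80%. Inflation: 44 × 1.15 = 50.6, rounded up to 51 per arm, 102 in total. Both figures reproduce.

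**4. How much a removal could matter at design size (illustration only)**

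The number removed, k, is an assumption. Take 51 randomised per arm, a common true rate p (no effect), and up to k Customizable subjects who would have had an SSC removed before the attempt. With i SOC events and j Customizable events, the analysed Customizable count is j′ = max(j − k, 0) out of m = 51 − (j − j′). The chance of a false finding for Customizable is the sum of the binomial probabilities of i and j over all outcomes with j′/m < i/51 and Fisher p < 0.05.

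| k | p = 35% | p = 20% |
|---|---|---|
| 0 | 1.6% | 1.4% |
| 1 | 2.7% | 2.9% |
| 2 | 4.2% | 5.5% |
| 3 | 5.7% | 9.1% |
| 5 | 10.6% | 22.7% |

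This is a worst case, since every removed subject is assumed to have had an event. As a single borderline example, take 18/51 events on SOC. Customizable at 9/51 gives p = 0.0715; with one event-bearing subject removed, 8/50 gives p = 0.0397.

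**5. How many subjects in this trial**

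SAP 5.2 gives 71 enrolled (36 Customizable, 35 SOC). SAP 10 gives 70 treated at the interim review. Taking enrolled to mean randomised, the gap is 71 − 70 = 1, or 1/71 = 1.4%. SAP 10 also refers to subjects enrolled after the review, so that one may have been treated later.

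**The case against.** Much of the case for leaving the text alone is fair, and it limits the point.

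- **Not attempting the dressing removes nobody by itself.** Both Protocol 5.2 and the ITT definitions require withdrawal. Protocol 10.3 says the assigned arm is to be used, and a subject given the other dressing stays in ITT as randomised (SAP 11). A reluctant surgeon creates an exclusion only by also withdrawing the subject. This stands, but Protocol 7.2 makes withdrawal available and Protocol 5.2 anticipates it.
- **A reader might infer that the subject vanishes from every analysis.** SAP 6.1 counts subjects randomised, by arm, with reasons for early withdrawal. The loss would be visible; it is the outcome comparison that lacks the subject.
- **A reader might infer that the outcome can never be recovered.** Protocol 7.2 and 6.10 contradict that. The supportable statement is that follow-up to Day 30 is not assured.
- **SAP 5.1 and 10 speak of all enrolled subjects.** That is general scope; the endpoint and safety tables follow the definitions in SAP 5.3.
- **A reader might use the interim counts to argue that one subject decides the result.** The SAP 10 rates imply 5/29 v 1/32 (p = 0.093), and one more Customizable event gives 6/30 v 1/32, p = 0.0496. That argument fails. It uses FAS denominators; 0.0496 lies above the SAP's 0.048; and the difference runs against Customizable, so no success claim is made or lost. On approximate ITT denominators, assuming no further events outside the FAS, 5/36 v 1/35 gives p = 0.20, 6/36 v 1/35 gives p = 0.11 and 5/36 v 2/35 gives p = 0.43. One subject changes no conclusion.
- **Enrolment has stopped**, so new follow-up rules cannot help this trial. That is true of Protocol 5.2, but not of the ITT definition or the reporting.

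**Conclusion.** The point holds as a fault in the population definition. What the plan calls ITT is conditional on an event after randomisation, the investigator can influence that event knowing the arm, and no effectiveness or safety population contains all randomised subjects. The documents permit such an exclusion. They do not show that one occurred, and nothing in them supports a suggestion that subjects were selectively removed.

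In this trial the reach is at most one subject on the reported figures, assuming that enrolled means randomised, and quite possibly none. The conclusion does not depend on the interim results. The design-size table shows only why a definition open to this matters with samples this small, and it rests on an assumed number of removals, all with events.

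**What to change.** - **Protocol 10.2.2 and SAP 5.3:** define ITT as every subject whose randomisation envelope was opened, analysed in the randomised arm. Keep the attempt-to-apply condition for the Safety population only.
- **Protocol 5.2:** for subjects randomised but untreated, replace the limited CRFs with the scheduled SSC and CRI assessments through Day 30, unless the subject withdraws consent.
- **This terminated trial:** report withdrawals before the attempt by arm with reasons, or state that there were none. Include any such subject in the ITT analysis with whatever SSC status is known.

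The cost is wording in three places, a few follow-up visits by subjects who had to be willing to attend all scheduled visits to enter (Protocol 4.1.1), and slight dilution of the ITT estimate by untreated subjects. For the trial as it stands, the work is one reconciliation of opened envelopes against treated subjects and one sentence in the report.
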